16.0 MULTICENTER REGULATORY REQUIREMENTS

Washington University requires that each participating site sends its informed consent document to be reviewed and approved by the Washington University Regulatory Coordinator (or designee) prior to IRB/IEC submission.

Site activation is defined as when the secondary site has received official written documentation from the coordinating center that the site has been approved to begin enrollment. At a minimum, each participating institution must have the following documents on file at Washington University prior to study activation:

- Documentation of IRB approval of the study in the form of a letter or other official document from the participating institution's IRB. This documentation must show

- which version of the protocol was approved by the IRB.
- Documentation of IRB approval of an informed consent form. The consent must include a statement that data will be shared with Washington University, including the Quality Assurance and Safety Monitoring Committee (QASMC), the DSMC (if applicable), and the Washington University study team.
- Documentation of FWA, signed FDA Form 1572 (if applicable), and the CVs of all participating investigators.
- Protocol signature page signed and dated by the investigator at each participating site.

The coordinating center Principal Investigator (or designee) is responsible for disseminating to the participating sites all study updates, amendments, reportable adverse events, etc. Protocol/consent modifications and IB updates will be forwarded electronically to the secondary sites within 4 weeks of obtaining Washington University IRB approval. Activated secondary sites are expected to submit protocol/consent/IB modifications to their local IRBs within 4 weeks of receipt unless otherwise noted. Upon the secondary sites obtaining local IRB approval, documentation of such shall be sent to the Washington University study team within 2 weeks of receipt of approval.

Documentation of participating sites' IRB approval of annual continuing reviews, protocol amendments or revisions, all SAE reports, and all protocol violations/deviations/exceptions must be kept on file at Washington University.

The investigator or a designee from each institution must participate in a regular conference call to update and inform regarding the progress of the trial.

APPENDIX A: ECOG Performance Status Scale

Grade	Description
0	Normal activity. Fully active, able to carry on all pre-disease performance without restriction.
1	Symptoms, but ambulatory. Restricted in physically strenuous activity, but ambulatory and able to carry out work of a light or sedentary nature (e.g., light housework, office work).
2	In bed <50% of the time. Ambulatory and capable of all self-care, but unable to carry out any work activities. Up and about more than 50% of waking hours.
3	In bed >50% of the time. Capable of only limited self-care, confined to bed or chair more than 50% of waking hours.
4	100% bedridden. Completely disabled. Cannot carry on any self-care. Totally confined to bed or chair.
5	Dead.

APPENDIX B: Neoadjuvant PD 0332991: Registration Worksheet

Protocol #:	Neoadjuvant PD 0332991 (HRPO# 201301106)	Patient Initials	_____ - _____ - _____
PI Name:		Institution Name:	
Registering MD name:		Site Number:	
Study Coordinator Name and Email:		Site Telephone #	

Please ensure the following are included with this form: (Please ensure all patient identification information is removed)

Corresponding Source Documentation for Inclusion/Exclusion

Menopausal Status	 Pre/Peri- menopausal	 Postmenopausal
DOB:	____ / ____ / ____	
Zip Code:	____ - ____ - ____ - ____	
Date endocrine therapy initiated:	____ / ____ / ____	
Local Ki67 after at least 2 weeks of endocrine therapy:	_____	
Planned Date Investigational Treatment Initiation:	____ / ____ / ____	
Date of signed informed consent:	____ / ____ / ____	

REGISTRATION INCLUSION CRITERIA		
	1. Clinical T2-T4c at diagnosis or screening, any N, M0 invasive ER+ (Allred Score at least 3 or > 1% ER positivity) and HER2 negative (0 or 1+ by IHC or FISH negative equivocal) breast cancer, by AJCC 7th edition clinical staging, with the goal being surgery to completely excise the tumor in the breast and the lymph node.	
Note: If the patient has invasive breast cancer that is ER pos, HER2 neg or equivocal, or DCIS in the contralateral breast, the patient is eligible. Multifocal diseases are not excluded.		
	2. Ki 67 > 10% by central testing after at least 2 weeks on neoadjuvant endocrine therapy.	
	3. Female \geq 18 years of age.	
	4. ECOG performance status of 0, 1 or 2	ECOG: _____ Date Assessed: _____
	5. If premenopausal, patient must be willing to comply with pregnancy requirements laid out in Section 5.5.	
6. Laboratory Values (Within 14 days of Registration)		
	Leukocytes \geq 3,000/mcL	Screening result: _____
	Absolute Neutrophil Count (ANC) \geq 1,500/mcL	Screening result: _____
	Platelets (Plts) \geq 100,000/mcL	Screening result: _____
	Total bilirubin \leq upper normal institutional limits	Screening result: _____ ULN: _____
	Alanine aminotransferase (ALT) and aspartate aminotransferase (AST) \leq 2.5 x upper limit of normal (ULN)	ALT screening result: _____ ULN: _____ AST screening result: _____ ULN: _____
	Serum creatinine \leq upper normal institutional limits	Screening result: _____ ULN: _____
	7. Able to understand and willing to sign an IRB-approved written informed consent document	

REGISTRATION EXCLUSION CRITERIA	
	1. Prior treatment of this cancer including: surgery, radiation therapy, or chemotherapy.
	2. Receiving any other investigational agents.
	3. Prior therapy with any Cdk4 inhibitor
	4. Any of the following in the previous 6 months: myocardial infarction, severe/unstable angina, coronary/peripheral artery bypass graft, symptomatic congestive heart failure, cerebrovascular accident, transient ischemic attack, symptomatic pulmonary embolism
	5. Uncontrolled intercurrent illness including, but not limited to ongoing or active infection, symptomatic congestive heart failure, unstable angina pectoris, uncontrolled symptomatic cardiac arrhythmia, psychiatric illness/social situations that would limit compliance with study requirements
	6. Pregnant/nursing.
	7. Unwilling to employ adequate contraception.
	8. Known HIV-positive on combination antiretroviral therapy.
	9. Known metastatic disease
	10. Current use of anticoagulation therapy
	11. Previous excisional biopsy of the breast cancer or sentinel lymph node biopsy
	12. Any condition that impairs patient's ability to swallow PD 0332991 tablets (e.g., gastrointestinal tract disease resulting in an inability to take oral medication or a requirement for IV alimentation, prior surgical procedures affecting absorption)
	13. History of allergic reactions attributed to compounds of similar chemical or biologic composition to PD 0332991 or other agents used in the study
	14. Correct QT (QTc) interval > 470 msec
	QTc: _____ Date: _____
	15.
	16. Current use or anticipated need for food or drugs that are known strong CYP3A4 inhibitors (i.e. grapefruit juice, verapamil, ketoconazole, miconazole, itraconazole, posaconazole, erythromycin, clarithromycin, telithromycin, indinavir, saquinavir, ritonavir, nelfinavir, lopinavir, atazanavir, amprenavir, fosamprenavir, nefazodone, diltiazem, and delavirdine) or inducers (i.e. dexamethasone, glucocorticoids, progesterone, rifampin, phenobarbital, St. John's wort).
	17.

Completed by: _____

Date: ____ / ____ / ____

Investigator Signature: _____

Date: ____ / ____ / ____

For Wash U Use Only

Screen Failure

Yes

No

Subject Identifier:

_____ - _____

Signature (Wash U designee):

_____ Date: ____ / ____ / ____

APPENDIX C: Adjuvant PD 0332991 Registration Worksheet

Protocol #:	Neoadjuvant PD 0332991 (HRPO# 201301106)	Patient Initials	_____ - _____ - _____
PI Name:		Institution Name:	
Registering MD name:		Site Number:	
Study Coordinator Name and Email:		Site Telephone #	

Please ensure the following are included with this form: (Please ensure all patient identification information is removed)

Corresponding Source Documentation for Inclusion/Exclusion

Menopausal Status	 Pre/Peri- menopausal	 Postmenopausal
DOB:	____ / ____ / ____	
Zip Code:	____ - ____ - ____ - ____	
Date endocrine therapy initiated:	____ / ____ / ____	
Planned Date Investigational Treatment Initiation:	____ / ____ / ____	
Date of signed informed consent:	____ / ____ / ____	
Patient ID for Neoadjuvant Trial:		

REGISTRATION INCLUSION CRITERIA		
	1. Derived benefit from PD 0332991 in the neoadjuvant setting in this trial.	
	2. ECOG performance status of 0, 1 or 2	ECOG: _____ Date Assessed: _____
	3. If premenopausal, patient must be willing to comply with pregnancy requirements laid out in Section 5.5.	
4. Laboratory Values (Within 14 days of Registration)		
	Leukocytes \geq 3,000/mcL	Screening result: _____
	Absolute Neutrophil Count (ANC) \geq 1,500/mcL	Screening result: _____
	Platelets (Plts) \geq 100,000/mcL	Screening result: _____
	Total bilirubin \leq upper normal institutional limits	Screening result: _____ ULN: _____
	Alanine aminotransferase (ALT) and aspartate aminotransferase (AST) \leq 2.5 x upper limit of normal (ULN)	ALT screening result: _____ ULN: _____ AST screening result: _____ ULN: _____
	Serum creatinine \leq upper normal institutional limits	Screening result: _____ ULN: _____
	5. Underwent surgery of the breast and axilla for curative intent. Date of Surgery: _____	
	6. At least 4 weeks post-completion of adjuvant chemotherapy and radiation therapy if indicated.	
	7. Patients who already started on adjuvant hormonal therapy are eligible under the following conditions: 
 For the 26 patients who enrolled in the initial cohorts and derived benefit from neoadjuvant PD 0332991 (C1D1 Ki67 $>2.7\%$ and C1D15 Ki67 $\leq 2.7\%$), adjuvant PD 0332991 should be initiated as soon as possible if adjuvant hormonal therapy has been initiated and the patient has completed radiation if indicated. For patients who enrolled in the endocrine resistant cohort and derived benefit from neoadjuvant PD 0332991 (C1D15 Ki67 $\leq 10\%$), adjuvant PD 0332991 should be initiated within 6 months or sooner after initiation of adjuvant hormonal therapy. 	
	8. Able to understand and willing to sign an IRB-approved written informed consent document	

REGISTRATION EXCLUSION CRITERIA	
	1. Any of the following in the previous 6 months: myocardial infarction, severe/unstable angina, coronary/peripheral artery bypass graft, symptomatic congestive heart failure, cerebrovascular accident, transient ischemic attack, symptomatic pulmonary embolism
	2. Uncontrolled intercurrent illness including, but not limited to ongoing or active infection, symptomatic congestive heart failure, unstable angina pectoris, uncontrolled symptomatic cardiac arrhythmia, psychiatric illness/social situations that would limit compliance with study requirements
	3. Pregnant/nursing.
	4. Unwilling to employ adequate contraception.
	5. Known HIV-positive on combination antiretroviral therapy.
	6. Known metastatic disease
	7. Any condition that impairs patient's ability to swallow PD 0332991 tablets (e.g., gastrointestinal tract disease resulting in an inability to take oral medication or a requirement for IV alimentation, prior surgical procedures affecting absorption)
	8. History of allergic reactions attributed to compounds of similar chemical or biologic composition to PD 0332991 or other agents used in the study
	9. Correct QT (QTc) interval > 470 msec
	QTc: _____ Date: _____
	10.
	11. Current use or anticipated need for food or drugs that are known strong CYP3A4 inhibitors (i.e. grapefruit juice, verapamil, ketoconazole, miconazole, itraconazole, posaconazole, erythromycin, clarithromycin, telithromycin, indinavir, saquinavir, ritonavir, nelfinavir, lopinavir, atazanavir, amprenavir, fosamprenavir, nefazodone, diltiazem, and delavirdine) or inducers (i.e. dexamethasone, glucocorticoids, progesterone, rifampin, phenobarbital, St. John's wort).
	12.

Completed by: _____

Date: ____ / ____ / ____

Investigator Signature: _____

Date: ____ / ____ / ____

For Wash U Use Only

Screen Failure

Yes

No

Subject Identifier: _____ - _____

Signature (Wash U designee): _____ Date: ____ / ____ / ____

APPENDIX D: Medication Diary – PD 0332991

Today's Date: _____

Agent: _____

Cycle: _____

Patient Name: _____

Study ID#: _____

INSTRUCTIONS TO THE PATIENT:

1. Take 1 mg pill one time daily for 21 days, followed by 7 days of rest (no pills).
2. Take PD 0332991 at approximately the same time each day with a meal. Swallow the tablets whole and do not chew them.
3. If you forget to take your dose before 6:00PM, then do not take a dose that day. Restart taking it the next day.
4. Avoid St. John's Wort, Seville oranges, grapefruit, grapefruit juice, grapefruit hybrids, pummelos, and exotic citrus fruits from 7 days before you start taking PD 0332991 and throughout the entire study.
5. Complete this drug diary form for each 28-day cycle.
6. Record the date, time (include AM or PM), and the number of tablets taken (for each strength).
7. If you have any questions or notice any side effects, please record them in the comments section. Record the time if you should vomit.
8. If you have any questions, please call the study coordinator.
9. Please return the forms to your physician or your study coordinator when you go to your next appointment.
10. Please bring your unused study medications and/or empty bottles with you to each clinic visit so that a pill count can be done.

Day	Date	What time was dose taken?	# of 100 mg tablets taken	# of 25 mg tablets taken	Comments
1					
2					
3					
4					
5					
6					
7					
8					
9					
10					
11					
12					
13					
14					
15					
16					
17					
18					
19					
20					
21					

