5.0 TREATMENT PLAN

5.1 Neoadjuvant Treatment

Treatment will be administered on an outpatient basis. Patients will be instructed to make use of medication diaries (Appendices D and E) to act as a records for administration of PD 0332991 and anastrozole. Appropriate dose modifications are described in Section 6.0. No investigational or commercial agents or therapies other than those described below may be administered with the intent to treat the patient's malignancy.

Cycle 0 (Only applicable for PIK3CA Mutant and WT cohorts)

Before Cycle 1 Day 1 starts, patients who enrolled in the PIK3CA mutant or WT cohort should have completed Cycle 0. Cycle 0 therapy is 28 days of anastrozole (1mg PO daily) and, if premenopausal, goserelin 3.6mg SC every 28 days.

Cycles 1-5

Treatment with PD 0332991 combined with anastrozole (and goserelin if premenopausal) is to be 4 28-day cycles followed by a fifth cycle of 10-12 days duration consisting of daily PD 0332991 and anastrozole, with the last dose of both drugs to be given the day before surgery.

REGIMENT DESCRIPTION				
Agent	Dose	Route	Schedule	Cycle Length
PD 0332991	125 mg	PO	Daily (Days 1-21)	Cycles 1-4: 28 days
Anastrozole	1 mg	PO	Daily (Days 1-28)	Cycle 5: 10-12 days
Goserelin*	3.6 mg	SC	Q28 days	Adjuvant treatment: 28 days

* only if premenopausal; although it is preferred to be given on Day 1 of each cycle, it may be administered any day of the cycle to accommodate the Q28-day cycle for goserelin.

PD 0332991 should be taken with food. Anastrozole should be taken daily with or without food.

For both PD 0332991 and anastrozole:

- If a patient misses a day's dose entirely, she must be instructed not to make it up the next day but just take her regular dose the following day.
- If a patient vomits anytime after taking a dose, she must be instructed not to make it up but to resume subsequent doses the next day as prescribed.
- If a patient inadvertently takes an extra dose during a day, she must be instructed to not take the next day's dose.

Special Considerations for Cycle 5

Cycle 5 Day 1 of PD 0332991 may be delayed by up to 3 weeks to allow ANC to recover to $\geq 1500/\text{mcL}$ and platelets to recover to $\geq 100,000/\text{mcL}$ and other treatment related AEs

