5.6 Duration of Therapy

If at any time the constraints of this protocol are considered to be detrimental to the patient's health and/or the patient no longer wishes to continue protocol therapy, the protocol therapy should be discontinued and the reason(s) for discontinuation documented in the case report forms.

In the absence of treatment delays due to adverse events, neoadjuvant treatment may continue for 4 cycles plus the fifth short cycle or one of the following criteria applies:

- Documented and confirmed disease progression or Ki67>10 % on C1D15
- Death
- Adverse event(s) that, in the judgment of the investigator, may cause severe or permanent harm or which rule out continuation of study drug
- General or specific changes in the patient's condition render the patient unacceptable for further treatment in the judgment of the investigator
- Suspected pregnancy
- Serious non-compliance with the study protocol
- Lost to follow-up
- Patient withdraws consent
- Investigator removes the patient from study
- The Siteman Cancer Center decides to close the study

Adjuvant treatment (in patients eligible to receive it) may continue for up to 23 cycles or until one of the following criteria applies:

- Documented and confirmed disease progression
- Death
- Adverse event(s) that, in the judgment of the investigator, may cause severe or permanent harm or which rule out continuation of study drug
- General or specific changes in the patient's condition render the patient unacceptable for further treatment in the judgment of the investigator
- Suspected pregnancy
- Serious non-compliance with the study protocol (missing 50% dosing in any cycle due to non-compliance or missing study required procedures due to non-compliance determined by site investigator)
- Lost to follow-up
- Patient withdraws consent
- Investigator removes the patient from study
- The Siteman Cancer Center decides to close the study

Patients who prematurely discontinue treatment for any reason will be followed as indicated in the study calendar.

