8.1.5 Dosage Form and Preparation

Medication will be provided in non-patient specific bottles containing either 125 mg, 100 mg, or 75 mg capsules. The patient number and the protocol number should be recorded on the bottle label in the spaces provided. Site personnel must ensure that patients clearly understand the directions for self-medication. Patients should be given a sufficient supply to last until their next study visit. Unused drug and/or empty bottles should be returned to the site at the next study visit. PD 0332991 is an agent that must be handled and administered with care. Patients should be instructed to keep their medication in the bottles provided and not transfer it to any other container. Due to possible unknown hazards associated with topical and environmental exposure to experimental agents, capsules must not be opened and/or emptied into any vehicle for oral ingestion; capsules must be swallowed intact.

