10.2 Neoadjuvant Study Treatment Calendar (ALL Cohorts)

	≤ 14 days prior to registration	C1D1 ^A	C1D15 ±1 day	C2-5 D1±3 days	3 (+/-1) days prior to surgery	Off Study - Progression	Surgery ^B	Post-surgery ^C
TREATMENT								
Anastrozole ^E		Daily until the day of surgery (if no progression)						
Goserelin ^E		Every 28 days (if no progression)						
PD 0332991 ^F		3 weeks on and 1 week off ^{G,T}			D/C			
CLINICAL ASSESSMENT								
H&P, PS	X	X		X		X		X
Clinical meas. of breast lesions ^J	X	X		X		X		Exam
Adverse event assessment	X	X		X		X		X
CBC + differential	X			X	X ^Y			X
Serum chemistry ^K	X			X				X
Serum pregnancy test ^L		X			X	X		
Drug compliance assessment				X				
EKG (lead II) ^N	X						X	
RADIOLOGY								
Mammogram and US of breast and axillary masses ^O	X ^H			X ^H		X		
SAMPLE COLLECTION								
Tumor biopsies ^R		X ^W	X ^P	X ^Q		X ^S	X	
Research blood ^R		X ^U	X ^{P,V}			X ^S	X	

- A. C1D1 office visit, labs, EKG, as well as pre-PD 0332991 tumor biopsies may be done within 14 days prior to C1D1.
- B. Please refer to section 5.1. Surgery occurs between Cycle 5 day 11 and day 13 in patients who received Cycle 5 treatment. In patients who did not receive Cycle 5 treatment, surgery occurs 3 to 5 weeks following the last dose of PD 0332991.
- C. 30-60 days post-surgery, then yearly to document recurrence and survival for 5 years.
- E. Anastrozole (and goserelin if premenopausal) should have been started at least 28 days prior to C1D1 **(only applies to PIK3CA Mutant and Wild Type cohorts).
- F. Patients will keep a pill diary (Appendix D).
- G. If C1D15 Ki67 is > 10%, patient will discontinue PD 0332991 and be observed for AEs 30-60 days following the last dose, then followed per protocol. Further treatment is at the discretion of the treating physician.
- H. Prior to start of PD 0332991 (within 12 weeks prior to registration) and at the end of cycle 4 before surgery.
- J. 2D measurements of the breast lesion should be performed. Using a standard cm calibrated caliper, tape or ruler, the longest axis and the perpendicular axis of the tumor are to be measured and recorded in metric notation. In patients with synchronous lesions, it is recommended that both lesions be measured and biopsied the same if they are both >1cm with at least one dimension; otherwise, the dominant mass is followed clinically and by Ki67

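### The PD 0332991 diary counts tablet strengths that do not match the supplied capsules, and its printed schedule does not describe Cycle 5

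*Combined protocol and SAP*

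**What the plan says.** Section 5.1 tells patients to use the diaries in Appendices D and E, and treats these as the administration record. Section 10.2, footnote F, repeats this for neoadjuvant treatment: "Patients will keep a pill diary (Appendix D"). Section 10.3, footnote D, does the same for adjuvant treatment. Both calendars schedule a drug compliance assessment.

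Appendix D asks for the number taken at each strength and prints two count columns, the number "of 100 mg tablets taken" and the number "of 25 mg tablets taken". Its schedule line reads "one time daily for 21 days, followed by 7 days of rest (no pills"), and one form is to be completed per 28-day cycle.

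Section 8.1.5 describes the supply as "non-patient specific bottles containing either 125 mg, 100 mg, or 75 mg capsules". Section 8.1.1 also describes capsules. Table 3 in Section 6.0 sets the daily dose levels at 125 mg (starting), 100 mg and 75 mg.

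Section 5.1 adds a "fifth cycle of 10-12 days duration consisting of daily PD 0332991 and anastrozole", with the last doses the day before surgery. Section 10.2, footnote T, states it as 10 to 12 doses of PD 0332991. The table of contents lists no other PD 0332991 diary.

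**The concern.** A dosing diary should let a patient copy down what she took in the units printed on her bottle. This one asks her to count units that, at the starting level, she has not been given. Two patients taking the same capsule on the same days can complete the form differently and yield different recorded doses.

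Three things depend on the record:

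- **Exposure and compliance data.** The compliance assessments in both calendars draw on the diary.
- **Patient clarity.** The strengths on the form disagree with the bottle, which is undesirable on any patient-facing dosing document.
- **Cycle 5 intake.** Section 2.0 explains that Amendment #5 added Cycle 5 to examine why Ki67 had risen at surgery after a break from PD 0332991. Ki67 at surgery falls under secondary objective 4. Interpreting it requires knowing who took the drug in the days before surgery.

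**Working it through.** The plan gives no figure to reproduce. The check compares passages and adds simple dose arithmetic.

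**Units.** Table 3 daily doses equal the supplied strengths one for one. One capsule per day is therefore an inference; Section 8.1.5 gives bottle strengths only.

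| Table 3 level | Supplied unit (8.1.5) | Matching diary column | How the columns can express it |
|---|---|---|---|
| 125 mg (start) | 125 mg capsule | none | 1 × 100 + 1 × 25 |
| 100 mg | 100 mg capsule | 100 mg | 1 × 100 |
| 75 mg | 75 mg capsule | none | 3 × 25 |

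The supplied unit matches a column at 1 of 3 levels. The 25 mg column matches no supplied unit.

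**Size of a plausible mis-entry.** Assume one capsule is taken on each of 21 days and entered as 1 in a single column. Recorded fraction = (21 × column strength) / (21 × capsule strength).

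- 125 mg capsule under 100 mg: 2100 / 2625 = 80%
- 125 mg capsule under 25 mg: 525 / 2625 = 20%
- 75 mg capsule under 100 mg: 2100 / 1575 = 133%
- 75 mg capsule under 25 mg: 525 / 1575 = 33%

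A patient who writes 1 + 1 at 125 mg, or 3 at 75 mg, records 100%. The error can therefore be nil, downward or upward, depending on how each patient reads the form.

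**Schedule.** The diary's 21 days on and 7 off agree with Section 5.1 for Cycles 1 to 4 and with Section 10.3 for adjuvant cycles. Cycle 5 has 10 to 12 dosing days and no rest week. If the form is used in Cycle 5, its instruction contradicts Section 5.1. If it is confined to 28-day cycles, as its own wording suggests, no diary is listed for Cycle 5.

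**The case against.** The strongest reply is that this is a template mismatch with little consequence. Much of it stands.

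- **The dose can be recorded.** A reader might infer that the form cannot capture the actual dose. The table above shows that every level can be written in 100s and 25s, and there is a comments field. The fault is ambiguity.
- **No treatment rule is tripped by the diary alone.** A reader might infer that mis-entries misclassify patients under the 80% row of Table 4 or the 50% stop in Section 5.6. The 80% row covers only shortfalls caused by adverse events possibly related to treatment. A reading of exactly 80% still meets it. One missed day would bring the reading to 20/21 × 80% = 76%, but neither a wrong column nor an ordinary missed day is an adverse-event shortfall. The other rule, "missing 50% dosing in any cycle due to non-compliance", sits only in the adjuvant list, concerns missed dosing, and is judged by the site investigator. A patient who took every scheduled capsule missed nothing, whichever column she used.
- **No overdose is instructed.** A reader might infer that the 25 mg column could lead a patient to take three 75 mg capsules. No count of three is printed, the columns record doses already taken, and instruction 1 says once daily.
- **The strength in instruction 1 is not safe evidence.** As extracted, that line reads 1 mg. Appendix E has fill-in blanks at the same place, so a blank may have been lost. Nothing here relies on it.
- **There are cross-checks.** Appendix D and Section 8.1.5 have unused drug and empty bottles returned, Appendix D provides for a pill count, Section 8.1.6 requires capsule accountability, and Section 11.0 calls for a treatment form every cycle.
- **The analysis is largely insulated.** Section 15 plans no dose-intensity or compliance analysis.

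These replies limit the consequences. They do not remove the disagreement over units, which starts in Cycle 1 at the starting dose, or the gap at Cycle 5.

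**Conclusion.** The point holds as an inconsistency in a patient-facing dosing record. Appendix D disagrees with Section 8.1.5 on units at two of the three dose levels, including the one at which treatment starts. Its schedule does not describe Cycle 5.

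The likely effect is inconsistent exposure records. Under single-column entry of one capsule a day, the recorded dose at the two unmatched levels would range from 20% to 133% of the planned dose; it would be correct if patients combine columns as the table shows. How often mis-entry would occur cannot be told from the documents. Pill counts and capsule accountability should catch much of it.

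No sample size, power, alpha or primary endpoint figure changes, because the primary analysis uses Ki67 at Cycle 1 Day 15 in eligible women who begin combination treatment and are evaluable. The correction is still worth making because the contradiction is plain, it concerns dosing instructions, and it costs little to remove.

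**What to change.** The sponsor should reconcile Appendix D with Section 5.1, Table 3, Section 8.1.5 and footnote T of Section 10.2, and confirm which units and which schedule apply. This review takes no position on which is right.

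The reissued diary should record the strength actually dispensed and the number of units taken, and should cover Cycle 5, either on the same form or on a separate one. For diaries already completed, the recorded dose should be verified against capsule accountability and pill counts before it is used in any exposure or compliance summary.

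The cost is one revised patient form and an IRB submission, plus the time to check completed diaries against records the protocol already requires.
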